| 
 • To characterize the antiviral response after a single dose or multiple doses of RO7565020 in virologically suppressed participants with CHB (Parts 2 and 3, respectively) | 
 • Change from baseline in serum quantitative HBsAg • Maximum reduction from baseline of serum HBsAg across all timepoints • Proportion of participants with HBsAg loss (on quantitative and qualitative HBsAg assays) • Proportion of participants with HBsAg seroconversion (sustained loss of HBsAg and detection of anti-HBs antibody) • Proportion of participants with hepatitis B e antigen (HBeAg) loss among HBeAg-positive participants at baseline • Proportion of participants with HBeAg seroconversion (sustained loss of HBeAg and detection of anti-HBe antibody) among HBeAg-positive participants at baseline |
| 
 • To assess the immunogenicity (induction of anti-drug antibodies [ADA]) of RO7565020 in healthy participants and virologically suppressed participants with CHB | 
 • ADA prevalence at baseline • Incidence and titer of ADA over time |

OVERALL DESIGN AND STUDY POPULATION

This FIH study of RO7565020 will be conducted in three parts: Part 1a is a Sponsor-open, Investigator-blinded, single-ascending dose (SAD) study in healthy participants with at least 8 participants per cohort. Part 1b is an optional, Sponsor-open, Investigator-blinded multiple-dose study with 8 healthy participants in 1 cohort. Part 2 is a SAD study in virologically suppressed participants with CHB with 6 participants in each cohort. Participants will be enrolled into Parts 2a and 2b on the basis of the screening HBsAg level (cutoff: 3000 IU/mL). Part 3 is an optional, multiple-dose study with 6 virologically suppressed participants with CHB per cohort.

RO7565020 will be administered via SC injection in healthy participants and participants with CHB, and via IV infusion over 2 hours to healthy participants only. In Parts 1a and 1b, participants will be randomized 6:2 to receive RO7565020 or placebo. In Parts 2 and 3, all participants will receive RO7565020 and all participants will continue to receive NUC therapy throughout the study. Sentinel dosing will be applied to each cohort. The sentinel participants will be monitored for at least 72 hours to confirm safety.

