| 
 To characterize the antiviral response after a single dose or multiple doses of RO7565020 in virologically suppressed participants with CHB (Parts 2 and 3, respectively) | 
 Change from baseline in serum quantitative hepatitis B surface antigen (HBsAg) Maximum reduction from baseline of serum HBsAg across all timepoints Proportion of participants with HBsAg loss (on quantitative and qualitative HBsAg assays) Proportion of participants with HBsAg seroconversion (sustained loss of HBsAg and detection of anti-HBs antibody) Proportion of participants with hepatitis B e antigen (HBeAg) loss among HBeAg-positive participants at baseline Proportion of participants with HBeAg seroconversion (sustained loss of HBeAg and detection of anti-HBe antibody) among HBeAg-positive participants at baseline |
| 
 To assess the immunogenicity (induction of anti-drug antibodies [ADAs]) of RO7565020 in healthy participants and virologically suppressed participants with CHB | 
 ADA prevalence at baseline Incidence and titer of ADA over time |
| Exploratory | |
| 
 To characterize the relationship between HBsAg at baseline, the serum concentration of RO7565020 and the maximum reduction of HBsAg (Parts 2 and 3) | 
 Model parameters describing relationships between ratio of RO7565020/HBsAg at baseline and maximum HBsAg reduction |
| 
 To explore the potential impact of ADA on safety and PK/PD after single dose or multiple doses of RO7565020 in healthy participants (Part 1) and virologically suppressed participants with CHB (Parts 2 and 3) | 
 Relationship between ADA, safety, and PK/PD |
| 
 To explore the effect of RO7565020 on other viral biomarkers, such as HBeAg (calculated), HBV RNA, hepatitis B core-related antigen (HBcrAg), total HBsAg after HBsAg:HBsAb complex dissociation, and HBsAg isoforms (Parts 2 and 3) | 
 Baseline and change from baseline in HBeAg (calculated), HBV RNA levels, HBcrAg levels, total HBsAg (after HBsAg:HBsAb complex dissociation), and distribution of HBsAg isoforms |

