| 
 To explore the relationship between baseline disease characteristics and efficacy/safety responses (Parts 2 and 3) | 
 Association of the primary and secondary endpoints with the HBV genotype, baseline HBeAg status, and baseline exploratory parameters (such as HBV RNA, HBcrAg, total anti-HBc, HBsAg isoforms) |

Table 5 Objectives and Endpoints (cont.)

| Objectives | Endpoints |
|--|--|
| Exploratory (cont.) | |
| 
 To explore the relationship between HBsAg decrease, HBsAg-HBsAb immune complex formation, and the recovery of the immune response (Parts 2 and 3) | 
 Baseline and change from baseline of cytokines and other soluble markers of immune activation and inflammation Changes in immune cell subsets and activation status (flow cytometry/ICS) and antigen-specific immune response (ELISpot/FluoroSpot) at baseline and post-treatment (PBMC samples) Baseline and changes from baseline in the transcriptional profile of immune cells subsets in peripheral blood (host gene sc-RNAseq) |
| 
 To explore the relationship between potential AEs and inflammatory cytokines released in healthy participants (Part 1) and participants with CHB (Parts 2 and 3) | 
 Association between cytokines and other soluble markers of immune activation and inflammation with AEs |
| 
 To monitor the potential emergence of RO7565020-resistant variants and their impact on efficacy/safety outcomes (Parts 2 and 3) | 
 Baseline and changes in free and total HBsAg over time in relationship to RO7565020 PK Baseline and changes from baseline in binding affinity of RO7565020 to HBsAg Baseline and changes from baseline in the clonality of the S gene sequences |

4. **STUDY DESIGN**

4.1 **OVERALL DESIGN**

An overview of the study design is provided in Section [1.2](#).

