4.2.3 Rationale for Biomarker Assessments

4.2.3.1 HBV Dynamic Biomarkers

RO7565020 is a human IgG1 neutralizing antibody, which showed potent and cross-reactive in vitro neutralization against all main circulating viral genotypes of HBsAg. Therefore, the main virological endpoint in this study relies on measuring HBsAg at timepoints defined in the SoA (Section 1.3).

Additional well-established HBV dynamic biomarkers for the assessment of HBV treatment outcomes will include the time course of anti-HBs levels and the evolution of the HBeAg and anti-HBe statuses. In participants who are HBeAg-positive at study entry, a validated research-use-only (RUO) semi-quantitative calculation may be used to follow the time course of serum HBeAg levels over time. In order to evaluate the formation of HBsAg:HBsAb complexes, an assay is being developed by the Sponsor that may be used to either directly quantify the immune complexes or measure HBsAg independently of the putative formation of complexes (i.e., total HBsAg post-dissociation of HBsAg:HBsAb complexes), as appropriate. Additionally, quantification of HBsAg may be measured using a second assay designed to either evaluate a potential bias of the HBsAg quantitative assay being used or to measure a change in the affinity of RO7565020 to escape mutants that might be selected for by therapy with RO7565020.

Several HBV biomarkers have recently emerged in the field that may further support the demonstration of improved virus control. These novel biomarkers will not be used to screen participants and will not have an impact on any clinical decisions or other endpoint evaluation.

Among these, pregenomic HBV RNA, which bypasses reverse transcription and is released in plasma, may provide a direct measure of the transcriptional activity of cccDNA. Consistent with this view, in NUC-treated participants with suppressed HBV DNA, the presence of detectable circulating HBV RNA signals an increased probability of HBV DNA rebound upon NUC cessation ([Wang et al. 2016](#); [Fan et al. 2020](#); [Seto et al. 2021](#); [Kaewdech et al. 2020](#)). In the course of this study, a validated real-time polymerase chain reaction-based investigational assay may be used to quantify HBV RNA.

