9.2 SAMPLE SIZE DETERMINATION

The sample size was determined by practical considerations and not based on statistical power calculations.

Approximately 48 to 56 healthy participants and 30 to 54 participants with CHB (depending on whether the optional cohorts are conducted) are planned to be enrolled in this study.

In Part 1a, 8 participants with 6:2 ratio (active treatment versus placebo) are planned to be enrolled into each cohort. Six cohorts are planned. Additional cohort(s) with intermediate dose level(s) is/are allowed.

In Part 1b, 8 participants with 6:2 ratio (active treatment versus placebo) are planned to be enrolled if considered to be necessary based on the data of Part 1a.

In Part 2a and 2b, 6 CHB participants (all active treatment) per dose cohort are planned to be enrolled. Seven cohorts are planned including 2 optional cohorts.

In the optional Part 3, 6 CHB participants (active treatment) in each cohort (≤ 2 cohorts) are planned to be enrolled if considered necessary based on the data of Parts 1 and 2.

Dose escalation decisions will be made based on data from 5 or 6 participants from each cohort. With 5 participants per dose cohort, there is an at least 80% chance to observe at least one AE that has an incidence rate of 28% in the population; with 6 participants per dose cohort, there is an at least 80% chance to observe at least one AE that has an incidence rate of 24% in the population.

Participants who discontinue study prematurely or withdraw consent from the study for non-safety reason may be replaced in order to obtain the required participant numbers for a dose decision. Additional participants may be enrolled in additional dose cohorts that assess lower or repeat doses. In Parts 2 and 3, except for the replacements, additional participants may be enrolled in some cohorts in case the variability in PK and PD is too high in participants with CHB.

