9.3 ANALYSIS SETS

For purposes of analysis, the following populations are defined in [Table 10](#).

Table 10 Analysis Sets

| Participant Analysis Set | Description |
|--------------------------|--|
| PD | The analyses of the viral dynamic response will include all participants with CHB who received at least one dose of study treatment (RO7565020 or placebo). Participants will be analyzed according to the treatment group to which they were randomized/assigned. |
| Safety | All participants randomized/assigned to study treatment and who received at least one dose of the study treatment, whether prematurely withdrawn from the study or not, will be included in the safety analysis. |
| PK | All participants who have received at least one dose of study treatment and who have data from at least one postdose sample will be included in the PK analysis set. Participants will be excluded from the PK analysis set if they significantly violate the inclusion or exclusion criteria, deviate significantly from the protocol, or if data are unavailable or incomplete which may influence the PK analysis. Excluded cases will be documented with the reason for exclusion. All decisions on exclusions from the analysis will be made prior to database closure. |
| Immunogenicity | Participants who had at least one ADA assessment will be included and analyzed according to the treatment they actually received. The relationship between ADA status and safety, efficacy, PK, and biomarker endpoints will be analyzed and reported descriptively via subgroup analyses. |

Abbreviations: ADA = anti-drug antibody; PK = pharmacokinetics; PD = pharmacodynamics.

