9.4 STATISTICAL ANALYSES

Statistical summaries will be descriptive in nature and will be reported separately for each part of the study within the CSR. All study participants who are randomized to receive placebo within one part will be pooled as respective placebo control groups for each part.

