9.4.5 Pharmacodynamic Analyses

Viral dynamic response analysis will be done for the participants with CHB enrolled in Part 2a, Part 2b, and Part 3, and will be based on the PD analysis set (see [Table 10](#)). Descriptive statistics will be utilized to summarize the viral dynamic response outcome

measure of serum HBsAg and HBeAg (Table 12), and the exploratory viral dynamic endpoints of HBV RNA, HBcrAg, total HBsAg, HBsAg isoform (Table 13).

Table 12 Viral Dynamic Response Statistical Analysis Methods

| Endpoint | Statistical Analysis Methods |
|-------------------------------------|---|
| HBsAg change from baseline | Time course profile: summary descriptive statistics by cohort (including mean, standard deviation, median, minimum, and maximum) (in log10 IU/mL and % change from baseline) at each timepoint. |
| Maximum reduction of HBsAg | Summary descriptive statistics by cohort (including mean, standard deviation, median, minimum, and maximum) (in log10 IU/mL and % reduction). |
| HBsAg loss and HBsAg seroconversion | Proportion of HBsAg loss and HBsAg seroconversion at each timepoint. Percentages are based on PD analysis set. |
| HBeAg loss and HBeAg seroconversion | Proportion of HBeAg loss and HBeAg seroconversion at each timepoint. Percentages are based on PD analysis set. |

Abbreviations: HBeAg = hepatitis B e antigen; HBsAg = hepatitis B surface antigen; PD = pharmacodynamic.

Table 13 Exploratory Viral Dynamic Response Statistical Analysis Methods

| Endpoint | Statistical Analysis Methods |
|---|--|
| Baseline and change from baseline of HBV RNA, HBcrAg, and total HBsAg | Time course profile: summary descriptive statistics by cohort (including mean, standard deviation, median, minimum, and maximum) (in log10 IU/mL) at each timepoint. |

Abbreviations: HBcrAg = hepatitis B core-related antigen; HBsAg = hepatitis B surface antigen; HBV = hepatitis B virus.

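### Table 12 takes HBeAg loss and seroconversion percentages over all treated CHB participants, although both endpoints are defined only among those HBeAg-positive at baseline

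*Combined protocol and SAP*

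**What the plan says.** The synopsis and Table 5 (Section 3) list two secondary HBeAg endpoints. The first is "Proportion of participants with hepatitis B e antigen (HBeAg) loss among HBeAg-positive participants at baseline". The second is "Proportion of participants with HBeAg seroconversion (sustained loss of HBeAg and detection of anti-HBe antibody) among HBeAg-positive participants at baseline". Both carry the same restriction to people who had the antigen at baseline.

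The analysis rule is in Section 9.4.5, Table 12: "Proportion of HBeAg loss and HBeAg seroconversion at each timepoint. Percentages are based on PD analysis set". The PD analysis set comes from Table 10 in Section 9.3: "The analyses of the viral dynamic response will include all participants with CHB who received at least one dose of study treatment". That definition does not mention HBeAg.

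Two other places show that baseline HBeAg status is expected to vary. An exploratory endpoint in Table 5 is "Association of the primary and secondary endpoints with the HBV genotype, baseline HBeAg status, and baseline exploratory parameters". Section 4.2.3.1 describes a calculation for a subset: "In participants who are HBeAg-positive at study entry, a validated research-use-only (RUO) semi-quantitative calculation may be used".

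**The concern.** A participant who is HBeAg-negative at baseline has no HBeAg to lose. Table 5 respects this by limiting both endpoints to those at risk, and Table 12 does not. If a programmer follows Table 12, every HBeAg-negative participant enters the denominator and the percentage falls for a reason unrelated to the drug.

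Two named secondary endpoints would then be reported for a population other than the one defined. A reader given only the Table 12 percentage could not work back to the defined value without the number HBeAg-positive at baseline. Table 12 also leaves open whether someone HBeAg-negative from the start could be counted in the numerator, which would push the figure the other way.

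**Working it through.** **The plan's own figures.** The plan gives no numerical value for the HBeAg endpoints. The only computed figures in Section 9 are the adverse-event detection chances in Section 9.2, and they reproduce: 1 − (1 − 0.28)^5 = 0.8065 and 1 − (1 − 0.24)^6 = 0.8073, both at least 80%. They do not depend on the HBeAg denominator.

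**Do the two denominators differ?** The criteria in Sections 5.2.1 and 5.2.2 cover HBsAg positivity and titre, HBV DNA, ALT and other items. None concerns HBeAg. With the mixed status foreseen in Table 5 and Section 4.2.3.1, the HBeAg-positive group will in general be smaller than the PD set. Nothing in Section 9.3 or 9.4.5 restores the restriction.

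**Inputs.**
- N, the PD set in the reported group. Section 9.2 says "In Part 2a and 2b, 6 CHB participants (all active treatment) per dose cohort are planned to be enrolled", so N = 6 per cohort. Part 2a has three cohorts (Section 4.1), so N = 3 × 6 = 18.
- m, the number HBeAg-positive at baseline. The documents do not give it, so every m below is an assumption.
- x, the number of those m with HBeAg loss. The examples use x = 1, also an assumption.

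Two reporting levels are shown because the HBeAg row, unlike the HBsAg change and maximum-reduction rows, does not mention cohorts, and Section 9.4 says "Statistical summaries will be descriptive in nature and will be reported separately for each part of the study within the CSR".

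**Formulas.** Defined endpoint = x/m. Table 12 as written = x/N = (x/m)(m/N). Since x cannot exceed m, the Table 12 figure cannot exceed m/N.

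| Group | N | m (assumed) | Table 12, 1/N | Defined, 1/m | Ceiling under Table 12, m/N |
|---|---|---|---|---|---|
| One cohort | 6 | 1 | 16.7% | 100% | 16.7% |
| One cohort | 6 | 2 | 16.7% | 50% | 33.3% |
| One cohort | 6 | 3 | 16.7% | 33.3% | 50% |
| Part 2a | 18 | 3 | 5.6% | 33.3% | 16.7% |
| Part 2a | 18 | 6 | 5.6% | 16.7% | 33.3% |
| Part 2a | 18 | 9 | 5.6% | 11.1% | 50% |

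**Boundary cases.** The two versions agree if m = N, or if x = 0 with m above 0. If m = 0 in a cohort, the defined endpoint is 0/0 and cannot be estimated, while Table 12 gives 0/6 = 0%, which reads as non-response.

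**The numerator.** If participants HBeAg-negative at baseline were counted as having lost the antigen, the figure would be (N − m + x)/N. With N = 6, m = 2, x = 1 this is (6 − 2 + 1)/6 = 83.3%, against 50% for the defined endpoint. With N = 18, m = 6, x = 1 it is (18 − 6 + 1)/18 = 72.2%, against 16.7%. No text directs this; it shows what an unspecified numerator would permit.

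**The case against.** The best defence is that Table 12 names an endpoint already defined in Table 5, so the restriction travels with the name and the PD set is only the source population. The protocol does use similar wording in that sense elsewhere, for instance for the safety analysis set in Section 9.4.2. This does not carry the point. Section 9.4.5 has already named the PD set for the whole analysis, and a further sentence about what percentages are based on is denominator wording. The same sentence closes the HBsAg loss row directly above, where it is right because every CHB participant must be HBsAg-positive at entry. It was probably carried down, which would make this a slip and not a deliberate change of population. Even on the lenient reading the row needs the same clarification.

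A second defence is that the planned association of secondary endpoints with baseline HBeAg status could reveal x and m. It might, but that analysis is exploratory and does not change the stated rule for the secondary endpoints.

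Three qualifications stand. Every m and x above is assumed. The inflated-numerator case has no support in the text beyond its silence. The importance is limited: no hypothesis is tested, and Section 4.2.3.1 makes HBsAg the main virological measure.

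**Conclusion.** The inconsistency is real, and Table 12 is wrong as written: it does more than omit a detail. It would shrink both HBeAg percentages by the factor m/N whenever an HBeAg-negative participant is enrolled and at least one HBeAg-positive participant responds. For example, one loss with two at risk in a cohort of 6 would be reported as 16.7% and not 50%. The size in practice depends on the baseline HBeAg-positive share and on whether any loss occurs, neither of which the documents give.

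The consequence is confined to two descriptive secondary endpoints. With so few participants at risk, neither version of the percentage supports a comparison of doses. It should be corrected before analysis so that the denominator is not chosen once results are known.

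**What to change.** Replace the closing sentence of the HBeAg row in Table 12 with: *Percentages (numerator and denominator) are based on participants in the PD analysis set who are HBeAg-positive at baseline.* Show that n beside each percentage, and report the endpoint as not estimable where n is zero. The HBsAg row can stay as it is.

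The cost is one sentence and one extra n per percentage. No new data should be needed, because Section 8.7.1 already plans qualitative HBeAg testing. While editing, check the serology row label in the Part 2 schedule (Table 3): in the text available it lists HBsAg where the Part 3 schedule (Table 4) lists HBeAg. That may be only a reading error from the PDF, and it is not part of this concern.

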9. STATISTICAL CONSIDERATIONS

9.1 STATISTICAL HYPOTHESES

No statistical hypothesis testing is planned for this study.

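### Table 12 summarises seroconversion visit by visit, with no persistence rule and no participant-level proportion, although Table 5 defines it through sustained antigen loss

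*Combined protocol and SAP*

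**What the plan says.** Section 3, Table 5, and the synopsis list two seroconversion endpoints among the secondary antiviral endpoints for Parts 2 and 3:

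- HBsAg: "Proportion of participants with HBsAg seroconversion (sustained loss of HBsAg and detection of anti-HBs antibody", with the bracket closing there.
- HBeAg: "Proportion of participants with HBeAg seroconversion (sustained loss of HBeAg and detection of anti-HBe antibody) among HBeAg-positive participants at baseline".

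The two antigen-loss endpoints in the same table do not require the loss to be sustained.

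Section 9.4.5, Table 12, gives loss and seroconversion one shared method per antigen: "Proportion of HBsAg loss and HBsAg seroconversion at each timepoint" and "Proportion of HBeAg loss and HBeAg seroconversion at each timepoint". Both rows take percentages on the PD analysis set. Table 10 defines that set as the dosed participants with CHB, without regard to HBeAg status.

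**The concern.** Persistence is part of what separates seroconversion from loss in Table 5, and Table 12 drops the distinction. A proportion computed separately at each visit looks at one visit only. Unless a rule links visits within a participant, it cannot show that a loss was sustained. No such rule is given, and no summary counts each participant once.

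Persistence matters for this drug. Section 4.3, Table 7, and the notes to Tables 3 and 4 extend follow-up only for participants whose HBsAg has not come back to baseline by Week 24. A temporary trough in HBsAg is therefore a foreseen course, and a trough is a different finding from sustained loss. Section 2.1 makes sustained loss part of functional cure, so a visit-wise figure labelled seroconversion invites over-reading. Two programmers could also derive different rates from the present text and both claim to have followed it.

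**Working it through.** The documents give no figure for seroconversion. The only calculated probabilities, in Section 9.2, concern adverse events. They reproduce, 1 − 0.72^5 = 0.8065 and 1 − 0.76^6 = 0.8073, and do not bear on this point. The check is therefore mainly textual.

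**1. Does the plan define persistence anywhere?** It does for other outcomes. Return of HBsAg to baseline needs two consecutive visits (notes to Tables 3 and 4). A persistent ADA response needs positive samples over 16 weeks or more, or a positive last sample (Section 9.4.4). Table 12 also gives maximum HBsAg reduction one summary per participant, not a time course. Seroconversion has neither a persistence rule nor a per-participant summary.

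**2. Can the endpoint be recovered from the visit-wise proportions?** No. Take one cohort ("In Part 2a and 2b, 6 CHB participants (all active treatment) per dose cohort are planned to be enrolled") in which Table 12 shows 1/6 = 16.7% on each of Days 113, 141 and 169. Two histories fit:

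- One participant is antigen-negative with antibody on all three days, a run of 169 − 113 = 56 days. The participant-level result is 1/6.
- Three different participants each have one such reading. The result is 0/6 if a run is required and 3/6 if any single visit counts. The participant first negative on Day 169 cannot yet be classified.

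The same Table 12 entries are compatible with 0/6, 1/6 or 3/6.

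**3. Would a bare rule of two consecutive visits be enough?** In Part 2, HBsAg is scheduled on 12 post-dose days: 2, 3, 4, 8, 15, 22, 29, 57, 85, 113, 141 and 169. Days 2, 3 and 4 are 24 hours apart, so the rule could be met within 48 hours of dosing. A minimum interval is needed.

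**4. HBeAg denominator.** With k of 6 participants HBeAg-positive at baseline and one seroconversion, Table 12 gives 1/6 and Table 5 gives 1/k:

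| k | Table 12 | Table 5 |
|---|---|---|
| 1 | 16.7% | 100% |
| 2 | 16.7% | 50% |
| 3 | 16.7% | 33.3% |
| 4 | 16.7% | 25% |
| 6 | 16.7% | 16.7% |

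**5. Illustration only.** Assume that a borderline participant has an isolated negative with probability q at each of 12 visits, independently, and that antibody is always present. None of this is in the documents. The chance of at least one negative visit is 1 − (1 − q)^12. The chance of two in a row comes from the recursion a′ = (a + b)(1 − q), b′ = aq, started at a = 1, b = 0 and run 12 times, as 1 − a − b.

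| q | At least one visit | Two in a row |
|---|---|---|
| 1% | 11.4% | 0.1% |
| 5% | 46.0% | 2.6% |
| 10% | 71.8% | 9.7% |

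These are cumulative chances for one participant. A visit-wise table would show about q at any one visit. The figures show that the choice of rule matters; they do not predict rates.

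**The case against.** Table 12 does not redefine seroconversion. It uses a term that Table 5 has already defined through sustained loss, so it can be read as the proportion meeting that definition by, or from, each visit. On a cumulative reading the last visit would give the participant-level proportion. This part of the objection stands: a reader might infer that the plan deliberately counts isolated negatives as seroconversion, and no section says so. The reading does not close the gap, because it still cannot be programmed while sustained is undefined, and Table 12 does not say that its proportions are cumulative.

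A reader might also infer large inflation of seroconversion rates from the illustration. The documents do not support that. The per-visit rates are assumed. Serial readings in one person, some a day apart, are unlikely to be independent. The antibody requirement would lower the figures. Entry requires HBsAg of at least 20 IU/mL in Part 2a and above 3000 IU/mL in Part 2b, so participants do not start near the limit of detection. The 16.7-point step is simply 1/6 and applies to any binary result in a cohort of 6.

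Two further points stand. The visit-wise layout is right for the loss endpoints that share these rows. The stakes are also limited: "No statistical hypothesis testing is planned for this study", "The sample size was determined by practical considerations and not based on statistical power calculations", and the stopping rules do not mention seroconversion.

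**Conclusion.** The point holds as a gap between endpoint and analysis. Table 5 states participant-level endpoints that require sustained loss. Table 12 plans visit-wise proportions and supplies neither a persistence rule nor a participant-level summary. Taken literally, it does not deliver the endpoint and leaves room for a transient negative to be reported as seroconversion at that visit. It cannot be said that the plan requires such readings to be counted, or by how much rates would change.

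The size is one participant in six, 16.7 points, per misclassified participant in a cohort. The HBeAg denominator mismatch rests on the text alone: for one converter, the Table 5 figure ranges from 16.7% to 100% according to how many of the six were HBeAg-positive at baseline, while Table 12 stays at 16.7%. The consequence is for interpretation of secondary, descriptive results only. The change should be made, but nothing in the design depends on it.

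**What to change.** Revise Table 12 as follows.

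- Keep the visit-wise proportion for antigen loss and, if wanted, a seroconversion time course labelled as a display.
- Add a participant-level seroconversion proportion by cohort.
- Pre-specify *sustained*. One option is antigen-negative at consecutive scheduled visits spanning a stated minimum nominal interval, such as 28 days, with no later return of antigen and with the matching antibody detected in that run. The 28 days is an example, not a figure from the documents. An interval in nominal days is safer than a count of visits, because early visits are a day apart, visits have windows, and the notes to Table 4 allow serology sampling in Part 3 to be thinned.
- State how missing visits and a first negative at the last visit are handled. In Part 2, a participant first HBsAg-negative on Day 169 goes into the additional visits every 56 days, so for HBsAg the last-visit case arises mainly with early termination or at the end of those visits. HBeAg has no such safeguard of its own.
- For HBeAg loss and seroconversion, use participants HBeAg-positive at baseline as denominator and show that number for each cohort.

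Fix the definition before Part 2 and Part 3 results are summarised, since those parts are open label. The cost is wording and one derived variable, with no new visits or samples. Reported seroconversion rates may be slightly lower than under a visit-wise count.
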